5.6.3 Clinical Laboratory Evaluation

5.6.3.1 Hematology and Biochemistry

Summaries will be presented by treatment arm for each laboratory parameter at each visit. Change from baseline to each post-baseline visit will also be presented.

If values for any of the parameters are below or above the limit of quantification of the assay (BLQ or ALQ), then they will be included in the summary tables at the BLQ or ALQ thresholds. However, for estimated creatinine clearance, results >60 are reported only as '>60'. Hence, estimated glomerular filtration rate (eGFR) will be calculated as:

For patients who are ≥ 18 years at screening, the Cockcroft-Gault equation will be used:

$$\text{eGFR (mL/min)} = [(140 - \text{age}) \times \text{weight} \times k] / \text{serum creatinine}$$

where age is measured in years, weight is measured in kg, $k = 1.23$ if male, $k = 1.04$ if female and serum creatinine is measured in $\mu\text{mol/L}$. eGFR will be indexed to body surface area (BSA) using the following formula:

$$\text{eGFR (mL/min/1.73m}^2\text{)} = \text{eGFR (mL/min)} \times 1.73/\text{BSA}$$

where BSA is based on the Du Bois and Du Bois formula:

$$\text{weight}^{0.425} \times \text{height}^{0.725} \times 0.007184$$

where weight is measured in kg and height is measured in cm.

For patients who are <18 years at screening, the revised Schwartz estimate will be used:

$$(36.2 \times \text{height}) / \text{serum creatinine}$$

where height is measured in cm and serum creatinine is measured in $\mu\text{mol/L}$. When available, enzymatic serum creatinine will be used. Otherwise, the Jaffe serum creatinine will be used. If height or weight is missing at the collection date, then the closest value to the sample date will be used. If there is more than one height or weight value on the same day or 2 height or weight values equally distant from the collection date, then the mean will be used. The eGFR will be summarized separately for each method.

Where laboratory samples are repeated, the baseline value is defined as the final recorded value prior to the first dose of IMP.

Shift tables for hematology and biochemistry parameters will be constructed, based upon normal ranges and GW toxicity limits (See Section 8), to determine the categorical shifts from baseline to each post-baseline visit. Values will be categorized as 'Normal', 'Low' or 'High' based on normal ranges and 'Toxically Low', 'Toxically Normal' or 'Toxically High' based on GW toxicity limits.

For eGFR, results will be assigned to the following grades:

- Normal: $>60 \text{ ml/min/1.73 m}^2$
- Grade 1: $60 \text{ ml/min/1.73 m}^2$
- Grade 2: ≥ 30 and $<60 \text{ ml/min/1.73 m}^2$
- Grade 3: ≥ 15 and $<30 \text{ ml/min/1.73 m}^2$
- Grade 4: $<15 \text{ ml/min/1.73 m}^2$

A separate shift table will be produced for eGFR based upon the above grades to determine the categorical shifts from baseline to each post-baseline visit.

For the blinded phase, scatter plots will be produced for each laboratory parameter presenting the maximum post baseline result divided by the upper limit of normal (ULN) on the Y-axis, and the baseline result divided by the ULN on the X-axis. However, for prothrombin international normalized ratio (INR), both axes will present the raw results rather than dividing by ULN.

An additional table will be produced for the blinded phase only, summarizing the number of patients meeting the following criteria:

- Alanine aminotransferase (ALT) $> 1 \times \text{ULN}$ at baseline
- Aspartate aminotransferase (AST) $> 1 \times \text{ULN}$ at baseline
- AT $> 1 \times \text{ULN}$ at baseline
- Treatment emergent ALT $> 3 \times \text{ULN}$, $> 5 \times \text{ULN}$ and $> 8 \times \text{ULN}$
- Treatment emergent AST $> 3 \times \text{ULN}$, $> 5 \times \text{ULN}$ and $> 8 \times \text{ULN}$
- Treatment emergent AT $> 3 \times \text{ULN}$, $> 5 \times \text{ULN}$ and $> 8 \times \text{ULN}$
- Treatment emergent AT $> 3 \times \text{ULN}$ and either bilirubin $> 2 \times \text{ULN}$ or INR > 1.5

where AT is AST or ALT, and treatment emergent is defined as criteria not met at baseline but met at any time post-baseline. The above will be summarized overall and for the following subgroups:

- Sex (Male, Female).

- Valproic acid use (Yes, No).
- Clobazam use (Yes, No).
- Valproic acid use and Clobazam use (Yes/Yes, Yes/No, No/Yes, No/No).
- Patients taking 3 or more current AEDs.
- Patients taking 4 or more current AEDs.

A separate table will be produced, by treatment arm and visit, presenting the incidence of patients with urinalysis or blood results indicative of a medical condition at Visit 1 and indicative of an adverse event after Visit 1.

All laboratory data will be listed; listings will include limited demographic information about the patient (age, sex, race and weight at baseline). Abnormal laboratory values will be listed separately.

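### The eGFR grades leave Grade 1 as the single value 60 and all higher values in one class, so the shift tables miss a halving from a baseline above 120

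*SAP*

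**What the plan says.** SAP Section 5.6.3.1 calculates eGFR because, for the laboratory's estimated creatinine clearance, "results >60 are reported only as" a capped value. Patients under 18 at screening get the revised Schwartz estimate, "36.2 \times \text{height}) / \text{serum creatinine", with height in cm and creatinine in µmol/L. For adults, Cockcroft-Gault is used, indexed to body surface area. No rule rounds eGFR before it is graded.

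The first three grades are:

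- "Normal: $>60 \text{ ml/min/1.73 m}^2"
- "Grade 1: $60 \text{ ml/min/1.73 m}^2"
- "Grade 2: ≥ 30 and $<60 \text{ ml/min/1.73 m}^2"

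Grade 3 runs from 15 to below 30, and Grade 4 is below 15. The section then states: "A separate shift table will be produced for eGFR based upon the above grades". The shifts run from baseline to each later visit. The outputs are Table 13.3.3 for the blinded phase and OLE Table 13.3.3 for the extension (SAP Appendix 6).

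**The concern.** A graded shift table should show patients whose kidney function moves between ordered levels. Here the mildest abnormal level is a point, so in practice the first visible step is from Normal straight to Grade 2. Everything above 60 is one level, which restores in the graded table the cap at 60 that led the SAP to calculate eGFR. A patient can lose a large share of a high baseline eGFR and still be tabulated as Normal to Normal.

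This matters because the SAP's rationale (Section 1.1) names the kidney among the organs in which TSC tumors mainly develop, and these two tables are the only categorical outputs specific to eGFR.

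**Working it through.** **Inputs.** The five grades and both eGFR formulas come from SAP Section 5.6.3.1. The SAP gives no distribution of baseline eGFR, so baselines from 61 to 180 are examined as an assumption. The patients below are illustrations.

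**Step 1: is Grade 1 really a point?** Normal is strictly above 60 and Grade 2 is strictly below 60. Only 60 remains. The two neighbouring grades force this, so it does not depend on a symbol lost before the 60.

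**Step 2: how often would eGFR equal 60?** In children this requires 36.2 × height = 60 × creatinine, that is 181 × height = 300 × creatinine. Since 181 and 300 share no common factor, whole-number values satisfy it only if height is a multiple of 300 cm. A count over heights 70 to 190 cm and creatinine 10 to 150 µmol/L (121 × 141 = 17,061 combinations) agrees:

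- unrounded: 0 values equal to 60;
- rounded to a whole number: 159 values, 159 / 17,061 = 0.9%.

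**Step 3: which falls stay hidden?** From a baseline b above 60, a proportional fall f leaves the patient in Normal when b × (1 − f) > 60, so f < 1 − 60/b. A halving stays hidden when b/2 > 60, that is b > 120.

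| Baseline | After halving | Grade after halving | Hidden falls are those below |
|---|---|---|---|
| 61 | 30.5 | Grade 2 | 1.6% |
| 80 | 40 | Grade 2 | 25.0% |
| 90 | 45 | Grade 2 | 33.3% |
| 100 | 50 | Grade 2 | 40.0% |
| 119 | 59.5 | Grade 2 | 49.6% |
| 120 | 60 | Grade 1 | 50.0% |
| 121 | 60.5 | Normal | 50.4% |
| 130 | 65 | Normal | 53.8% |
| 150 | 75 | Normal | 60.0% |
| 180 | 90 | Normal | 66.7% |

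**Step 4: the SAP's own formulas with creatinine doubled.**

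- Child, 110 cm, creatinine 30 to 60: 36.2 × 110 / 30 = 132.7, then 36.2 × 110 / 60 = 66.4. No shift.
- Child, 160 cm, creatinine 45 to 90: 128.7 to 64.4. No shift.
- Child, 120 cm, creatinine 40 to 80: 108.6 to 54.3. Normal to Grade 2.
- Man, 25 years, 70 kg, 175 cm, creatinine 70 to 140: 132.4 to 66.2. No shift.
- The same man, creatinine 80 to 160: 115.9 to 57.9. Normal to Grade 2.

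**Step 5: does the creatinine toxicity table fill the gap?** Its limit is 2.6 times the upper limit of normal (Appendix 4, Table 12). A creatinine that starts at or below that upper limit and doubles reaches at most 2 times it, so this table cannot flag such a doubling.

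**The case against.** A reader might infer that the table hides any halving from a healthy level. The grades do not support that: from any baseline above 60 and below 120 a halving lands in Grade 2, and from exactly 120 it lands in Grade 1.

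Nor is the information lost from the report:

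- Continuous laboratory summaries include the minimum and maximum (SAP Section 5.1), and change from baseline is summarised at each visit. The largest absolute fall per arm and visit will therefore appear.
- Biochemistry shift tables based on reference ranges (Table 13.2.2 and its OLE counterpart) may move creatinine from Normal to High. The reference limits are not in the SAP, so whether the examples above would be caught is unknown.
- The blinded-phase scatter plot (Figure 14.1.4.2.X) would put a doubled creatinine at twice its baseline as an individual point.
- All laboratory data are listed.

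These replies stand, and they show that only the graded display is coarse. They do not repair it. Extreme values and arm-level summaries do not count patients. A reference-range shift depends on crossing a limit, not on the size of the fall. The scatter plots use the maximum post-baseline result, which is the wrong direction for eGFR itself, and the OLE figure list (Table 22) contains seizure figures only. Listings tabulate nothing.

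It is also tempting to say that the OLE primary endpoint is compromised. It is not: that endpoint is the incidence, type and severity of adverse events (Section 3.3.1), and laboratory parameters are secondary safety measures.

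**Conclusion.** The point holds in a limited form. Grade 1 as written is practically empty for a calculated eGFR, and one class covers everything above 60. The two eGFR shift tables show no shift for a halving from a baseline above 120, for a fall of just under 40% from 100, or for a fall of just under one third from 90. Other outputs offset this in part, but no planned table counts patients by size of eGFR fall.

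How many patients would be affected cannot be derived, because the SAP gives no baseline eGFR distribution. The near-empty Grade 1 assumes that eGFR is graded unrounded or rounded to a whole number. This is a minor weakness in a descriptive safety display: the grades are exhaustive and do not overlap, and no hypothesis test or efficacy result depends on them.

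**What to change.** In SAP Section 5.6.3.1, reconcile the Normal and Grade 1 boundaries so that Grade 1 is a range with lower bound 60 and an upper bound that the sponsor specifies and justifies, for example the lower limit of the reference range. The SAP supplies no such limit, so none is proposed here. State whether eGFR is rounded before grading.

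Add to Tables 13.3.3 and OLE 13.3.3 the number of patients with a post-baseline fall in eGFR beyond pre-specified percentages of baseline, for example at least 25% and at least 50%. Compare values only within the same creatinine method, since the section allows enzymatic or Jaffe results. These counts need no upper limit for Grade 1 and would show large falls above 60 whatever boundary is chosen.

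The cost is a change of wording and two reprogrammed tables, with no new data. The downside is that more patients will appear in Grade 1 at baseline.

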5.6.4 Vital Signs, Other Physical Findings and Other Safety Data

5.6.4.1 Vital Signs

At Visit 1, 3 and B3, systolic and diastolic blood pressure are collected in the sitting, supine and standing positions. At all other visits, systolic and diastolic blood pressure are collected in the sitting position only.

Summaries will be presented by treatment arm for each vital sign parameter at each visit. Change from baseline to each post-baseline visit will also be presented.

Body mass index will be calculated, for each visit in which height and weight are recorded, as:

$$\text{Weight (kg)} \div \text{height (m)}^2$$

A separate table will be produced, by treatment arm and visit, presenting the incidence of patients with vital signs indicative of a medical condition at Visit 1 and indicative of an adverse event after Visit 1.

Based on the criteria presented in Section 8, clinically significant changes from baseline in vital signs measurements and other defined flagged values will be identified at each visit. The number of patients with a clinically significant change from baseline will be summarized by parameter, visit and treatment arm. The number of patients with at least one post-baseline flagged vital sign parameter value will be summarized by parameter, flagged criteria and treatment arm for the blinded phase and repeated for the OLE phase.

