Appendix 4 Toxicity Criteria for Laboratory Parameters

The toxicity criteria that will be used to identify abnormal laboratory parameters are presented in Table 12 and

Table 13.

Table 12 Toxicity Criteria for Biochemistry Parameters

Parameter	Toxicity Decrease	Toxicity Increase
Chloride	≤0.96xLL	≥1.04xUL
Calcium	≤0.89xLL	≥1.16xUL
Sodium	≤0.96xLL	≥1.04xUL
Potassium	≤0.90xLL	≥1.10xUL
Glucose (mmol/L)	≤3.2	≥16
Phosphate	≤0.79xLL	
Cholesterol	≤0.85xLL	≥1.6xUL
AST		≥3xUL
ALT		≥3xUL
Lactate Dehydrogenase		≥2.6xUL
Alkaline phosphatase		≥2xUL
Gamma GT		≥2.6xUL
Bilirubin		>2xUL
Albumin	≤0.84xLL	
Total protein	≤0.84xLL	≥1.16xUL
Urea		≥2.6xUL
Blood urea nitrogen		≥2.6xUL
Creatinine		≥2.6xUL
Uric acid		≥1.16xUL

UL = upper limit of reference range

LL = lower limit of reference range

Table 13 Toxicity Criteria for Hematology Parameters

Parameter	Toxicity Decrease	Toxicity Increase
Hemoglobin (g/dL)	≤9.4	
Hematocrit (%)	≤28	
Red cell count	≤0.84xLL	
Mean corpuscular volume	≤0.84xLL	≥1.11xUL
Mean corpuscular hemoglobin	≤0.84xLL	
Mean corpuscular hemoglobin concentration	≤0.84xLL	
Platelets (x10 ⁹ /L)	≤74	
Prothrombin time		>1.5xUL
Prothrombin international normalized ratio		>1.5
Total white blood cell count (x10 ⁹ /L)	≤2.9	≥21
Total neutrophil count (x10 ⁹ /L)	≤1.36	≥14.7
Segmented neutrophil count (x10 ⁹ /L)	≤0.75	≥12.3
Eosinophils (x10 ⁹ /L)		≥1.5
Basophils (x10 ⁹ /L)		≥0.31
Monocytes (x10 ⁹ /L)		≥2.1
Lymphocytes (x10 ⁹ /L) for patients <18 years (auto hematology)	≤1.0	
Lymphocytes (x10 ⁹ /L) for patients <18 years (manual hematology)	≤0.2	
Lymphocytes (x10 ⁹ /L) for patients ≥18 years	≤0.2	

UL = upper limit of reference range

LL = lower limit of reference range

Appendix 5 Derivation Instructions for Achenbach Child Behavior Checklists and Adult Behavior Checklist

CBCL/1½–5

The syndrome scale and problem scale grouping of items is shown in Table 14. If data are missing for more than 8 items (not counting item 100) then the syndrome and problem scales will not be calculated.

Each of the items is scored 0, 1 or 2 as indicated on the questionnaire. The individual items associated with each syndrome scale are presented in Table 14.

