Table 11.14	Summary of Non-Serious Treatment Emergent Adverse Events by Event	Safety Analysis Set
Table 12.1	Summary of Serious Treatment Emergent Adverse Events	Safety Analysis Set
Table 12.2	Summary of Treatment-Related Serious Treatment Emergent Adverse Events	Safety Analysis Set
Table 12.3	Summary of Treatment Emergent Adverse Events Leading to Permanent Discontinuation of IMP	Safety Analysis Set
Table 12.4	Summary of Treatment-Related Treatment Emergent Adverse Events Leading to Permanent Discontinuation of IMP	Safety Analysis Set

Table Number	Title	Analysis Set
Table 12.5	Summary of Treatment Emergent Adverse Events Leading to IMP Dose Reduction Excluding Permanent Discontinuation and by Resolution and Overall	Safety Analysis Set
Table 12.6	Summary of Treatment-Related Treatment Emergent Adverse Events Leading to IMP Dose Reduction Excluding Permanent Discontinuation and by Resolution and Overall	Safety Analysis Set
Table 12.7	Summary of Treatment Emergent Adverse Events Leading to Temporary IMP Dose Reduction by Resolution and Overall	Safety Analysis Set
Table 12.8	Summary of Treatment-Related Treatment Emergent Adverse Events Leading to Temporary IMP Dose Reduction by Resolution and Overall	Safety Analysis Set
Table 12.9	Summary of Treatment Emergent Adverse Events Leading to Permanent IMP Dose Reduction Excluding Permanent Discontinuation and by Resolution and Overall	Safety Analysis Set
Table 12.10	Summary of Treatment-Related Treatment Emergent Adverse Events Leading to Permanent IMP Dose Reduction Excluding Permanent Discontinuation and by Resolution and Overall	Safety Analysis Set
Table 12.11	Summary of Fatal Treatment Emergent Adverse Events	Safety Analysis Set
Table 12.12	Summary of Serious Treatment Emergent Adverse Events by Event	Safety Analysis Set
Table 12.13	Summary of Treatment-Related Serious Treatment Emergent Adverse Events by Event	Safety Analysis Set
Table 13.1.1	Summary of Laboratory Safety Parameters – Hematology	Safety Analysis Set
Table 13.1.2	Summary of Laboratory Safety Parameters – Biochemistry	Safety Analysis Set
Table 13.2.1	Shift Table for Hematology Laboratory Parameters – Based on Reference Ranges	Safety Analysis Set
Table 13.2.2	Shift Table for Biochemistry Laboratory Parameters – Based on Reference Ranges	Safety Analysis Set
Table 13.3.1	Shift Table for Hematology Laboratory Parameters – Based on Toxicity Limits	Safety Analysis Set

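### The only worst-value plot for general laboratory data shows the maximum, and no table counts patients with at least one toxically low or high value after baseline

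*SAP*

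**What the plan says.** SAP Section 5.6.3.1 plans several displays for hematology and biochemistry.

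- **Scatter plots, blinded phase only:** "scatter plots will be produced for each laboratory parameter presenting the maximum post baseline result divided by the upper limit of normal (ULN", against the baseline result on the same scale. INR is the one exception. It is plotted unscaled, but still as a maximum. The figure list in Appendix 6 (Figures 14.1.4.1.X and 14.1.4.2.X) also names only the maximum after first dose.
- **Shift tables:** results are classed as "Toxically Low', 'Toxically Normal' or 'Toxically High' based on GW toxicity limits", and separately as low, normal or high against reference ranges. The purpose is "to determine the categorical shifts from baseline to each post-baseline visit". The toxicity versions are Tables 13.3.1 and 13.3.2, with OLE equivalents.
- **Liver table:** patients who newly meet ALT, AST, bilirubin or INR criteria at any time after baseline are counted. All these criteria are elevations.
- **Incidence table (13.5):** by arm and visit, for results judged indicative of an adverse event.
- **Listings:** abnormal values by patient and by parameter.

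The limits are in Appendix 4, Table 12 ("Toxicity Criteria for Biochemistry Parameters") and Table 13 ("Toxicity Criteria for Hematology Parameters").

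For vital signs, Section 5.6.4.1 goes further: "The number of patients with at least one post-baseline flagged vital sign parameter value will be summarized". Section 5.6.4.2 does the same for ECG.

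**The concern.** The SAP defines toxic falls for most of its laboratory parameters, but its one general worst-value display looks only upward. A patient whose platelets fall to a toxic level at one visit and recover is plotted at the highest later value, much like a patient who had no event.

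The quantity a safety reader would compare between arms is the number of patients who were ever toxically low, or ever toxically high, after baseline. The SAP produces this kind of count for vital signs, ECG and liver tests, but not for the Appendix 4 limits. Without it, arms have to be compared one visit at a time, on small numbers.

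**Working it through.** The SAP states no figure on this point, so there is nothing to reproduce. The check is a count of the limits, a comparison of the displays, and two illustrations on stated assumptions.

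**1. Direction of the limits (Appendix 4, lymphocytes counted once)**

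| | Parameters | Decrease only | Both | Increase only |
|---|---|---|---|---|
| Table 12 | 19 | 2 | 7 | 10 |
| Table 13 | 16 | 7 | 4 | 5 |
| Total | 35 | 9 | 11 | 15 |

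A decrease limit exists for 9 + 11 = 20 of 35. The nine decrease-only parameters are phosphate, albumin, hemoglobin, hematocrit, red cells, MCH, MCHC, platelets and lymphocytes.

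**2. One patient followed through the displays**

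Take invented post-baseline hemoglobin values of 12.5, 12.3, 9.0 and 12.4 g/dL. Table 13's limit is 9.4 g/dL or lower.

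- Scatter plot: the maximum is 12.5, so the fall does not appear.
- Table 13.3.1: the patient is toxically low at the third visit.
- Any planned table counting the patient once as ever toxically low: none.

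**3. How little a one-visit fall moves the plot**

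Assume k post-baseline samples and one baseline sample, independent with the same distribution. The SAP does not give k for laboratory samples, so a range of 4 to 7 is shown.

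- No event: the chance that the maximum exceeds baseline is k/(k+1). This gives 4/5 = 80%, 6/7 = 86% and 7/8 = 88% for k = 4, 6 and 7.
- One very large fall at one visit: only k−1 samples can supply the maximum, so the chance is (k−1)/k. This gives 3/4 = 75%, 5/6 = 83% and 6/7 = 86%.
- With normal variation and k = 6, the mean of the plotted maximum is +1.16 within-patient SD with the fall and +1.27 SD without it (simulation).
- With a sustained fall of 1 SD at every visit, 51% to 61% still plot as increased for k = 4 to 7 (59% at k = 6; simulation).

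The 86% with no event is a property of any maximum and would apply to ALT as well. The relevant contrast is 86% against 83%: a large transient fall is almost invisible.

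**4. Why by-visit cells do not give the per-patient count**

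Let n be patients per arm, q the chance of a toxically low value at a visit, and K the number of visits. Each visit shows about nq patients. The number ever affected lies between nq (the same patients every time) and n[1 − (1 − q)^K] (independent visits). Here n = 70 is from SAP Section 3.2; q and K are assumed.

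- q = 2%, K = 5: per visit 70 × 0.02 = 1.4. Ever affected: from 1.4 to 70 × (1 − 0.98^5) = 6.7.
- Over q = 1% to 5% and K = 4 to 7: 0.7 to 3.5 per visit, and 2.8 to 21.1 ever affected if visits are independent.

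The same by-visit tables fit either end of each range.

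**The case against.** A reader might infer that toxic falls are hidden, or that no table counts the patients who have them. The SAP does not support that.

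- "Shift Table for Hematology Laboratory Parameters – Based on Toxicity Limits" (Table 13.3.1) and its biochemistry counterpart put such a patient in the toxically low cell for the arm and visit.
- Section 5.1 requires a minimum and maximum in continuous summaries. The lowest value and the largest fall at each visit are therefore tabulated by arm.
- Abnormal values are listed by patient. Falls reported as adverse events are counted per patient across the phase.

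A reader might also infer that unscheduled samples reach only a listing. The SAP does not say so. Its repeat-sample rule covers baseline only, and it is silent on how unscheduled post-baseline samples enter the by-visit tables.

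Nor does the SAP call rises in the nine decrease-only parameters harmless. It still classes them as high against reference ranges.

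It can fairly be added that the scatter plot is supplementary, is plainly titled as a maximum and supports no test or decision rule, and that shift tables with listings are a coherent safety presentation.

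All of this stands, and it limits the point. It does not supply the missing count. The incidence table is by visit and depends on judgment rather than on the Appendix 4 limits. Adverse event tables depend on the fall having been reported as an event. The by-visit minimum shows the worst value, not the number of patients affected.

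**Conclusion.** The point holds in a limited form. The maximum-over-ULN plot cannot show a transient toxic fall, although the SAP sets a decrease limit for 20 of 35 parameters and only a decrease limit for 9. No planned output counts patients with at least one toxically low or high value after baseline against the Appendix 4 limits, and the by-visit tables cannot be added up to give it.

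The parameter counts come straight from Tables 12 and 13. The percentages for the plot assume independent samples, with normal variation where simulated. The 1.4 to 6.7 range rests on assumed visit numbers and risks. None of these estimates how many toxic falls would be overlooked, since the by-visit tables and listings would still show them.

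This is a low-cost improvement to safety reporting. Efficacy results, Type I error and the recorded data are unaffected.

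**What to change.** Two changes to Section 5.6.3.1 and the output list, using the Appendix 4 limits as they stand:

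1. For each parameter with a decrease limit, plot the minimum post-baseline result divided by the lower limit of normal against the baseline result divided by the lower limit of normal. Where both limits exist, keep the maximum plot as well.
2. Add a worst post-baseline row to Tables 13.3.1 and 13.3.2 and their OLE equivalents, with low and high separate. Count patients with at least one value in the category who were not in it at baseline, and state that all post-baseline samples are used, including unscheduled ones.

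The cost is some SAP wording, a few figure panels and a few table rows from data already collected. No dose or clinical rule is touched.
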